If Cohort III data determines the 200×10^6 cell dose to be safe, the Phase 2 patients may be switched to receive the 200×10^6 cell dose, infused three times at intervals of at least 2 weeks.

In Cohorts IV and V, patients will receive three consecutive doses of MT-401, manufactured using the accelerated process, at a fixed dose of 100×10^6 cells and 200×10^6 cells, respectively, in fused at intervals of at least 2 weeks. The dose determined to be safe at the conclusion of Cohorts IV and V will determine the final Phase 2 dose.

Confidential Page 14 of 74

Statistical Methods

Analysis Populations:

All enrolled patients: All patients who sign the ICF and donor undergoes leuk apheresis..

All randomized patients in Phase 2 (Adjuvant - Group 1 only): All patients in Group 1 who are randomized with the final dose and manufacturing process and are MRD prior to randomization by central testing and local testing (if a local test was also performed). Efficacy analyses for Group 1 will be conducted in this population. A patient randomized based on negative MRD result per central test but confirmed to be MRD will be excluded from Group 1 analyses. The patient will be included in Group 2 Subgroup D analyses if treated with MT-401.

All treated patients: All patients who receive at least one dose of MT-401 or were randomized to SOC. Patients whose product includes fewer cells or does not meet specifications may still be treated, but will be summarized separately from patients whose product meets specifications. For Group 1 (adjuvant therapy), sa fety analyses will be conducted in this population, and sa fety data for patients randomized to SOC will also be shown for reference. For Group 2 (active disease), the primary and secondary efficacy analyses and safety analyses will be conducted in this population. For the Safety Lead-in (Cohorts I and II) and Cohorts III-V, all efficacy and safety analyses will be conducted in this population.

DLT-evaluable: All patients in the Safety Lead-in (Cohorts I and II) and Cohorts III-V who receive at least one dose of MT-401 and have had the opportunity to be followed for 28 days from the initial MT-401 infusion or have experienced a DLT.

Per-protocol in Phase 2: All treated patients, as defined above, who have no major protocol deviations. Select efficacy analyses for Group 1 and Group 2 will be conducted in this population for sensitivity analysis.

Planned Analysis:

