A minimum of 3 patients each will be treated in Cohorts I and II; if 1 patient experiences a DLT related to MT-401, 3 additional patients will be treated in the cohort (see Section 5.6). If overall, 0 out of 3 patients or 1 out of 6 patients experience a DLT in the specific cohort, this dose will be established as safe for the Phase 2 portion of the study (see Section 5.6). Additional patients may be treated to acquire data such as biomarkers as long as no safety issues arise. In the event that > 1 patient, experiences a DLT (see Section 5.6) related to MT-401, then no further patients will be treated in that cohort. A new cohort of patients will be treated at a lower dose level (DL1) with a flat dose of 25 x 10⁶ cells (Cohorts -I or -II). Dose Level 1 will be repeated with an additional 3-6 patients once new peptides are synthesized for use during manufacturing (Cohort II). If Cohort II is deemed safe for patients, this dose and peptide manufacturer will be used in the Phase 2 portion of the study. In parallel to opening the Phase 2 portion of the study, Cohorts III-V will open to enroll patients using the same standard 3+3 design described above for Cohorts I and II.

Patients who initially receive any dose of MT-401, but are subsequently deemed unevaluable (e.g., important protocol deviation, starting investigational drugs not approved by the Sponsor) and removed from the study will not count as DLTs in the Safety Lead-in and Cohorts III-V and may need to be replaced.

Confidential Page 33 of 74

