5.2. Patient Exclusion Criteria

Patients are excluded from the study if any of the following criteria apply:

- 1. Clinically significant or severely symptomatic intercurrent infection
- 2. Pregnant or lactating
- 3. Any other issue which, in the opinion of the treating physician, would make the patient ineligible for the study
- 4. For Group 1, anti-neoplastic therapy after HSCT and prior to or during dosing of MT-401
- 5. For Group 2, concomitant anti-neoplastic therapy during or after dosing of MT-401

Confidential Page 35 of 74

- 6. Evidence of acute or chronic GVHD ≥Grade 2 (exception: acute or chronic Grade 2 GVHD of skin allowed if stable) within one week prior to receiving MT-401
- 7. Taking systemic corticosteroids (exception: physiological doses of steroids allowed)
- 8. On other investigational therapy post-HSCT
- 9. Anti-thymocyte globulin or Campath within 28 days of MT-401 infusion

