6.5.1. Prohibited Concomitant Medications

Patients should not receive other antineoplastic agents or systemic steroids. Physiologic doses of systemic steroids (e.g., for adrenocortical insufficiency) are allowed before or after MT-401. For patients in Group 2, bridging therapy prior to MT-401 infusion is permitted as described in eligibility.

If steroids are received outside parameters specified in protocol, the patient may be considered unevaluable.

Patients should not be administered any live vaccines while on study unless prior approval from Sponsor is obtained.

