7. DISCONTINUATION OF MT-401 AND PARTICIPANT DISCONTINUATION/WITHDRAWAL

7.1. Discontinuation of MT-401

If it becomes necessary for a patient to permanently discontinue MT-401, the patient will remain in the study to be evaluated for safety, response, and survival. See the SoA (Table 1) for data to be collected at the time of intervention discontinuation and follow-up and for any further evaluations that need to be completed.

The following criteria will result in the patient being ineligible for further treatment on the protocol, although safety and response data will continue to be collected as applicable:

- Any patient who develops a DLT. In such patients, the toxicity will be followed until resolution or until their off-study date.
- Any patient who receives any other hematopoietic cell product (e.g., donor leukocyte infusion) except for routine blood product transfusions such as platelets and packed red blood cells. In such patients, AE data collection will cease.
- Any patient who enrolls in another clinical study involving investigational product or other type of medical research judged not to be scientifically/medically compatible with this study or receives antineoplastic treatment for relapse of their primary malignancy within 4 weeks after the T cell infusion. In such patients, adverse event data collection will cease.
- Refusal of the patient to continue treatment or observations.
- Decision by the investigator that discontinuation of treatment is in the patient's best medical interest
- Unrelated medical illness or complication deemed significant by the investigator.

• Death.

Confidential Page 41 of 74

- Progressive Disease.
- Lost to follow-up.
- At the request of Marker Therapeutics, Inc.
- Any patient who becomes pregnant.

Any new clinically relevant finding should be reported as an AE.

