9.2. Populations for Analyses

Populations for analyses are defined in Table 8.

Table 8. Populations for Analysis

Population	Description
All enrolled patients	All patients who sign the ICF and donor undergoes leukapheresis
All randomized patients in Phase 2 (Adjuvant - Group 1 only)	All patients in Group 1 who are randomized with final dose and manufacturing process, and are MRD prior to randomization by central testing and local testing (if a local test was a lso performed). Efficacy analyses for Group 1 will be conducted in this population. A patient randomized based on negative MRD result per central test but confirmed to be MRD will be excluded from Group 1 analyses. The patient will
All treated patients	be included in Group 2 Subgroup D analyses if treated with MT-401. All patients who receive at least one dose of MT-401 or were randomized to SoC. Patients whose product includes fewer cells or does not meet specifications may still be treated, but will be summarized separately from patients whose product meets specifications. For - Group 1, safety analyses will be conducted in this population, and safety data for patients randomized to SoC will also be shown for reference. For - Group 2, all efficacy analyses and safety analyses will be conducted in this population. For the Safety Lead-in (Cohorts I and II) and Cohorts III-V, all efficacy and safety analyses will be conducted in this population.
DLT-eva luable	All patients in the Safety Lead-in (Cohorts I and II) and Cohorts III-V who receive at least one dose of MT-401 and have had the opportunity to be followed for 28 days from the initial MT-401 infusion or have experienced a DLT.
Per-protocol in Phase 2	All treated patients, as defined above, who have no major protocol deviations. Select efficacy analyses for Group 1 and Group 2 will be conducted in this population for sensitivity analysis.

Confidential Page 51 of 74

Abbreviations: DLT=dose-limiting toxicity; ICF=informed consent form; MRD=minimal residual disease; SoC=standard of care

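### DLT-evaluable status requires only the chance of 28 days' follow-up, and excluding or replacing a patient whose adverse event collection stopped early is left to discretion

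*Protocol*

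**What the plan says.** Protocol Section 9.2 (Table 8) defines the DLT-evaluable set as Cohort I-V patients with at least one dose who "have had the opportunity to be followed for 28 days from the initial MT-401 infusion or have experienced a DLT". The synopsis words it the same way: "receive at least one dose of MT-401 and have had the opportunity to be followed for 28 days from the initial MT-401 infusion", or a DLT.

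Section 4.5 applies the 3+3 rule. A dose is established as safe if "0 out of 3 patients or 1 out of 6 patients experience a DLT in the specific cohort". Patients who have been dosed but are later deemed unevaluable and "removed from the study will not count as DLTs in the Safety Lead-in and Cohorts III-V and may need to be replaced". The two examples given are an important protocol deviation and the start of investigational drugs that the sponsor has not approved.

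Section 7.1 lists events that end MT-401 treatment. Its lead-in says that the patient becomes ineligible for more MT-401, "although safety and response data will continue to be collected as applicable". Two bullets are stricter. One stops adverse event collection after any other hematopoietic cell product, with donor leukocytes as the example. The other stops it after entry to an incompatible study or antineoplastic treatment for relapse of the "malignancy within 4 weeks after the T cell infusion. In such patients, adverse event data collection will cease".

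Section 4.3.1 says that all treated lead-in patients will be observed for 28 days before safety is established, but gives no rule for observation that is cut short. SAP 7.4.7.3 evaluates DLTs in the DLT-evaluable set. SAP 7.2 defines the all-treated, all-randomized and per-protocol populations and does not define this one.

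**The concern.** The DLT window and the events that stop adverse event collection overlap. Cohorts I-V take patients of the Group 2 type, with active disease, for whom donor leukocytes or rescue therapy in the first month is foreseeable. Table 8 still admits such a patient, because the opportunity for 28 days' follow-up existed when they were dosed.

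A 3+3 cohort can pass on three patients. One partly observed patient is then a third of the evidence, and the plan does not say in advance whether that patient counts. The decision could be made when the rest of the cohort's results are already known. The count contributes to confirming the peptide vendor (Cohorts I-II) and to the optional switch to 200 x 10^6 cells or to the accelerated process (Cohorts III-V).

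**Working it through.** **Step 1: does the text let a partly observed patient count?** The three triggers in Section 7.1, set against the Section 4.5 exclusion:

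| Trigger that stops AE collection | Covered by Section 4.5? |
|---|---|
| Entry to an incompatible study | In part: unapproved investigational drugs are a named example |
| Antineoplastic treatment for relapse within 4 weeks | It can be. Section 5.2 excludes "For Group 2, concomitant anti-neoplastic therapy during or after dosing of MT-401" and Section 6.5.1 says "Patients should not receive other antineoplastic agents or systemic steroids", so it fits an important deviation |
| Other hematopoietic cell product | Not named; the list of examples is open |

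For all three, exclusion needs someone to deem the patient unevaluable and remove them from the study, and replacement is optional. Section 7.1 says that a patient who permanently stops MT-401 stays in the study, so removal is not automatic. As written, the patient can stay in the count as DLT-free.

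**Step 2: which DLTs could go unseen?** By Section 5.6 criterion:

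- Criterion 1 (Grade 3-4 GVHD): GVHD has its own assessments (Section 8.2.1).
- Criterion 2 (CRS): any grade is reported within 24 hours (Section 8.3.1).
- Criterion 3 (infusion reaction lasting over 72 hours): almost moot, because no MT-401 infusion follows a trigger.
- Criterion 5 (death): captured.
- Criterion 4 (other prolonged Grade 3-4 toxicity): serious events fall under the reporting of all SAEs from Baseline to Week 12 (Section 8.3.1). Non-serious ones may be lost. Criterion 4 also sets aside toxicity due to treatment of disease, so attribution is less clear after salvage even when an event is seen.

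**Step 3: how much could the pass probability move?** The documents give no operating characteristics for the 3+3 and no early-salvage rate. Their only DLT data by dose are none in 2 patients at Phase 1 dose level 4 and none in 1 at dose level 5 (Section 4.3.2). The rest is assumed. Let p be the true 28-day DLT risk, with constant hazard over the window. Let s be the share of patients whose AE collection stops on a uniformly random day, and d the share of later DLTs still detected.

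Full observation: pass = (1-p)^3 + 3p(1-p)^2 x (1-p)^3. At p = 0.20 this is 0.512 + 0.384 x 0.512 = 0.7086.

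With stopping: the chance of a DLT before a random stop is r = 1 - p/L, where L = -ln(1-p). This gives r = 0.051, 0.104 and 0.178 at p = 0.10, 0.20 and 1/3. The observed risk is p' = (1-s)p + s[r + d(p-r)], which replaces p in the pass formula. At p = 0.20, s = 0.10, d = 0: p' = 0.180 + 0.0104 = 0.1904, and pass = 0.7294.

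| Case | p = 10% | p = 20% | p = 1/3 |
|---|---|---|---|
| Full observation | 90.6% | 70.9% | 42.8% |
| s = 10%, d = 0.5 | 91.0% | 71.9% | 44.3% |
| s = 10%, d = 0 | 91.4% | 72.9% | 45.8% |
| s = 20%, d = 0.5 | 91.4% | 72.9% | 45.8% |
| s = 20%, d = 0 | 92.2% | 75.0% | 49.0% |

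From unrounded values, the rise at s = 10% is 0.8, 2.1 and 3.0 points with d = 0, and 0.4, 1.0 and 1.5 points with d = 0.5.

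If the event has happened to one of the first three patients, at Day 10, that patient's observed risk is q = q0 + d(p-q0), with q0 = 1 - (1-p)^(10/28). Then pass = (1-p)^2(1-q) + [2p(1-p)(1-q) + (1-p)^2 q](1-p)^3. With d = 0.5 this gives 91.7%, 73.8% and 47.2%; with d = 0, 92.8%, 76.7% and 51.6%. These figures describe a cohort in which the event has occurred, not the average cohort.

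**The case against.** The strongest reply is that the plan mostly deals with this already. Section 4.5 has an unevaluable-and-replace rule with open-ended examples. It names unapproved investigational drugs, and early salvage is prohibited and so can be treated as an important deviation. Section 4.3.1 states the intent to observe for 28 days. This stands as far as it goes: the sponsor has the means to exclude these patients. It does not make exclusion or replacement a rule, and donor leukocytes are not named.

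A reader might infer that the patient goes unobserved once adverse event collection stops. The documents do not support that. Safety data continue as applicable, and the routes in Step 2 remain open. Whether the stop in Section 7.1 also ends SAE reporting is not stated, so the d = 0 rows are a worst case.

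A reader might also infer that any error favours calling the cohort safe. Missed events do, but there is an opposite error. Section 2.1 recognises that unmanipulated donor T cells can cause GVHD, and Section 5.6 counts Grade 3-4 GVHD that is even possibly related to MT-401. GVHD after donor leukocytes could therefore be wrongly charged to MT-401. The calculation models only missed events.

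Finally, the 3+3 count does not mechanically set the Phase 2 regimen. Section 9.3.1 adds the entirety of the safety data, Section 9.4 a sponsor review committee and Section 9.5 multiple parameters. The initial Phase 2 dose comes from Phase 1 (Section 4.3.2). This stands, and it is why the point is minor.

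**Conclusion.** The point holds as a minor flaw in a stated rule. DLT-evaluable status rests on the opportunity for follow-up, adverse event collection can stop inside the window, and keeping the affected patient out of the count is discretionary. The main problem is an observation that cannot be interpreted: events may be missed, mainly non-serious prolonged Grade 3-4 toxicity under criterion 4, and GVHD after donor leukocytes may be misattributed.

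The average effect is small. At an assumed stopping rate of 10%, the pass probability rises by at most about 0.8 to 3.0 points over true DLT risks of 10% to one third, and by about half that if half of later DLTs are seen. These figures rest on assumed stopping and detection rates and a constant hazard; the effect would be smaller if toxicity comes early. The documents do not show that any cohort was affected, or that a dose was wrongly declared safe. The missing definition in SAP 7.2 is a gap to close and does not by itself show a wrong count. The 28-day window is not in question.

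**What to change.** In Table 8 and the synopsis, define DLT-evaluable as at least one dose of MT-401 plus completed 28-day DLT observation, or a DLT. In Section 4.5, state that patients whose DLT observation ends early without a DLT are left out of the 0/3 and 1/6 counts and are replaced. Carry the same definition into SAP 7.2. A per-patient listing of infusions and days of adverse event observation for the sponsor review committee would show, for any completed cohort, whether the situation arose.

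The cost is wording in four places and one listing. The downside is an occasional replacement patient, which delays that cohort's decision by at least the 28-day window plus manufacturing time.

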9.3. Statistical Analyses

The SAP will be finalized before database lock and will describe the patient populations to be included in the analyses, and procedures for accounting for missing, unused, and spurious data. This section is a summary of the planned statistical analyses of the primary and secondary endpoints.

The primary analysis of the study will occur when 90 RFS events have occurred in Phase 2 Group 1. The clinical study report will be written based on this analysis. If the primary analysis of either Group 1 or 2 occurs after the primary analysis of the other group, an addendum to the CSR will be written to describe the results of the other group.

Categorical variables will be summarized as counts and percentages. Continuous variables will be summarized with univariate statistics, including mean, median, range, and standard deviation. Confidence intervals (CIs) will be calculated for summary statistics, addressing the primary and secondary efficacy outcomes.

The primary analysis will include disease assessments associated with the first treatment regimen of MT-401 only. Any disease outcomes collected subsequent to re-treatment (i.e. re-dosing) will be analyzed separately.

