9. STATISTICAL CONSIDERATIONS

9.1. Sample Size Determination

9.1.1. Adjuvant Population (Group 1)

A total of approximately 150 Group 1 patients will be randomized with a 1:1 allocation to receive MT-401 or to be under observation (SoC arm). Median RFS for the SoC arm is expected to be approximately 8 months (Rashidi et al, 2016; Goyal, 2016). A clinically meaningful increase in median RFS for the MT-401 arm over SoC is thought to be 2 months or more. The primary analysis will be conducted when 90 RFS events have been observed. Ninety (90) RFS events provides 80% power with alpha=0.05 to detect a median RFS improvement of 6.5 months over the assumed SoC median RFS of 8 months (hazard ratio=0.55). Ninety RFS will be observed assuming uniform accrual of 150 patients (75 per arm) over a 50-month period and an additional 12-month minimum follow-up period. The DMC and Sponsor will review data from Phase 2 based on the planned interim analyses described in Section 9.5.

If the decision is made to dose patients in Phase 2 with any of the MT-401 dosing regimens evaluated in Cohorts III-V, enrollment will continue in Phase 2 Group 1 to achieve 150 evaluable patients randomized and approximately 75 patients treated with the final MT-401 dose and the intended manufacturing process, thereby replacing any patients that have not been treated with the final Phase 2 product, as determined by the Sponsor.

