9.5. Interim Analyses

Safety Lead-in (Cohorts I and II) and Cohorts III-V: Safety data will be reviewed at the end of the Safety Lead-in to determine if it is appropriate to move forward with the specific peptide manufacturer in the Phase 2 portion of the study. The evaluation of DLTs will be conducted in the DLT-evaluable set. Safety data will also be reviewed at the end of Cohort III to determine if it is appropriate to switch to a higher dose in the Phase 2 portion of the study. Additionally, safety data will also be reviewed at the end of Cohorts IV and V to determine if it is appropriate to switch to a dosing regimen with the MT-401 product manufactured using the accelerated process in the Phase 2 portion of the study. This decision will be made by the Sponsor based on multiple parameters, including the safety and biomarker data available.

9.5.1. Phase 2 Group 1: One interim analysis is planned for Group 1.

The first interim analysis of Group 1 will occur when 45 RFS events have occurred in Group 1. It is anticipated that this will occur approximately 30 months after the first patient randomized. At this analysis, the DMC will assess safety, futility, and potential expansion of study accrual according to the criteria defined in the DMC charter. At the time of this analysis, enrollment of the remaining patients will continue, unless any safety concerns are identified.

9.5.2. Phase 2 Group 2:

After the first approximately 10 patients in each subgroup in Group 2 have progressed or had the opportunity to be followed for 6 months, clinical safety and efficacy will be reviewed comprehensively. Further enrollment for a subgroup may be terminated due to futility based on totality of the data. Patients

Confidential Page 57 of 74

treated in cohorts IV-V with the same manufacturing process as Group 2 may be included in Group 2 Subgroup C or Subgroup D analyses for decision making.

Details of the interim analysis will be described in the SAP, including pre-specified rules for futility and potential expansion of Group 1 enrollment and methods for control of the overall type I error rate.

Upon review of this interim analysis, the DMC may recommend adding additional patients to Group 2 based on the emerging data from the historical control study and the observed response rate at the interim analysis.

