7.2 Analysis Populations

The analysis populations are defined as follows:

- All Treated Patients: Includes all patients who received at least one dose of MT-401 or were randomized to SOC.
- All Randomized Patients: Includes all patients in Group 1 who were randomized with final dose and manufacturing process and are MRD⁻ prior to randomization by central testing and local testing, if a local test was also performed. A patient randomized based on negative MRD result per central test but confirmed to be MRD⁺ will be excluded from Group 1 analysis.

When MRD testing occurs with different methodology (eg, flow cytometry and PCR), the patient is considered MRD⁺ if either test detects MRD. If adjudication occurs between central testing and local testing for the same type of testing (eg, flow by central testing and flow by local testing), the final adjudicated result will be taken into account for the confirmed MRD result. A patient confirmed to be MRD⁺ prior to randomization will be excluded from Group 1 and will be included in Group 2 analysis if treated with MT-401.

- Per-Protocol (PP) Population: Includes all treated patients, as defined above, who have no major protocol deviations. If there is <5% difference in the all randomized patient population and the PP population for Group 1, no analyses will be performed on the PP population.

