7.6 Determination of Sample Size

Approximately 6-12 patients are expected to be enrolled in the Safety Lead-in portion of this study per a standard 3+3 design with 2 planned cohorts. In addition, approximately 9-18 patients (3-6 patients per cohort) are expected to be treated in the Cohorts III-V portion of this study as per a standard 3+3 design.

A total of 150 Group 1 patients will be randomized with a 1:1 allocation to receive MT-401 or to be under observation (SOC arm). Median RFS for the SOC arm is expected to be approximately 8 months. A clinically meaningful increase in median RFS for the MT-401 arm over SOC is thought to be 2 months or more. The primary analysis will be conducted when 90 RFS events have been observed. Ninety (90) RFS events provides 80% power with alpha=0.05 (two-sided) to detect a median RFS improvement of 6.5 months over the assumed SOC median RFS of 8 months (hazard ratio=0.55). Ninety RFS will be observed assuming uniform accrual of 150 patients (75 per arm) over a 50-month period and an additional 12 month minimum follow-up period. The DMC and Sponsor will review data from Phase 2 based on the planned interim analyses described in [Section 7.4.7.3](#).

If the decision is made to dose patients in Phase 2 with any of the MT-401 dosing regimens evaluated in Cohorts III-V, enrollment will continue in Phase 2 Group 1 to achieve 150 evaluable patients randomized and approximately 75 patients treated with the final MT-401 dose and the intended manufacturing process, thereby replacing any patients that have not been treated with the final Phase 2 product, as determined by the Sponsor.

A total of approximately 60 Group 2 patients are planned to be enrolled and treated with MT-401, 30 patients in Subgroup C (frank relapse patients) and 30 patients in Subgroup D (MRD⁺). After approximately 10 patients in each subgroup have progressed or had the opportunity to be followed for 6 months, clinical safety and efficacy will be reviewed comprehensively. Patients who develop CR_{MRD-} after bridging therapy and patients who relapse early (defined as less than 90 days ± 10 days and termed Group 2 Early Relapse patients) will be analyzed separately, and not be counted as part of the 60 patients in Group 2.

The sample size of 30 per subgroup is not based on a formal power calculation. An increase in the CR rate of greater than 10-15% compared to historical rates for standard of care would be considered clinically meaningful.

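### The 45- and 90-event triggers are not tied to the RFS analysis set, so a product change after Group 1 randomization starts could leave the primary test with fewer than 90 events and under 80% power

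*Protocol*

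**What the plan says.** **Triggers.** For the primary analysis, Protocol 9.3 and the synopsis say: "The primary analysis of the study will occur when 90 RFS events have occurred in Phase 2 Group 1". For the interim, Protocol 9.5.1 says: "The first interim analysis of Group 1 will occur when 45 RFS events have occurred in Group 1". Protocol 4.1 and SAP 6.1 likewise place the DMC review after the first 45 RFS events in Group 1. SAP 7.4.4 and 7.4.7.3 give 90 and 45 events without saying in whom they are counted.

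**Analysis set.** Protocol Table 8 (9.2) defines the Group 1 efficacy population as "All patients in Group 1 who are randomized with final dose and manufacturing process", with a further MRD-negative condition. SAP 7.2 matches: "Includes all patients in Group 1 who were randomized with final dose and manufacturing process". SAP 7.4.1 runs Group 1 efficacy in that set.

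**Power.** Protocol 9.1.1: "Ninety (90) RFS events provides 80% power with alpha=0.05". SAP 7.6 adds that the test is two-sided.

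**Product change.** Phase 2 opens on the initial dose and process while Cohorts III to V run in parallel (Protocol 4.1). The Sponsor may change the Phase 2 regimen after Cohort III, and again after Cohorts IV and V (Protocol 4.3.2). Protocol 9.1.1 and SAP 7.6 then continue Group 1 enrollment to 150 evaluable patients, replacing those not treated with the final product. Neither passage mentions events.

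**The concern.** Log-rank power depends on the number of events in the test. Both documents define the analysis set as a subset of Group 1, while the Protocol attaches the triggers to Group 1. If the product changes after Group 1 patients have been randomized, the two counts separate. Pre-switch patients have the longest follow-up, so they supply more than their share of the first 45 and first 90 Group 1 events, and those events would not enter the test.

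Two decisions are exposed. The primary RFS test could run before it has the events its power calculation needs. At the interim, the futility rule (hazard ratio above 1.1) and the 50% and 80% conditional-power limits in SAP 7.4.7.3 were set for 45 of 90 events and could be applied to fewer.

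**Working it through.** **Inputs from the documents.** 90 events, 1:1 allocation, two-sided alpha 0.05, SoC median 8 months, improvement 6.5 months (so 14.5 months), "hazard ratio=0.55", and uniform accrual of 150 patients over 50 months (3 per month, 1.5 per arm) plus 12 months' minimum follow-up.

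**Assumptions, because the documents are silent.** Exponential RFS; the switch month; the loss rate; which arms are dropped.

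**1. The plan's own figure.** Power = Φ(|ln HR| × √d / 2 − 1.96). With HR = 8/14.5 = 0.552 and d = 90: 0.5947 × 4.743 − 1.96 = 0.861, giving 80.5%. With HR = 0.55 it is 80.9%. The stated 80% is reproduced. There is little slack: at HR 0.552, 89 events give 80.1% and 88 give 79.7%; at HR 0.55, 88 give 80.1% and 87 give 79.6%. Losing two or three events is enough to fall below 80%.

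**2. Event model.** In one arm with hazard λ and loss hazard c, patients accrued uniformly at rate r over a months and followed for a further F months yield r·a·[λ/(λ+c)]·{1 − [e^(−(λ+c)F) − e^(−(λ+c)(a+F))]/[(λ+c)a]} expected events. The hazards are ln2/8 = 0.0866 (SoC) and ln2/14.5 = 0.0478 (MT-401). With c = 0, the 45th Group 1 event falls at about month 28 and the 90th at about month 44.9.

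**3. Month-6 switch, no loss.** There are 1.5 × 6 = 9 pre-switch patients per arm, with F = 44.9 − 6 = 38.9.
- SoC: 9 × [1 − (0.0344 − 0.0204)/0.520] ≈ 8.8 events.
- MT-401: 9 × [1 − (0.1557 − 0.1169)/0.287] ≈ 7.8 events.
- Both arms dropped: 90 − 16.5 ≈ 73 analysed events, power 72%.
- Only MT-401 dropped: 90 − 7.8 ≈ 82 events, power 77%.

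**4. Matching the plan's schedule.** With no loss the model expects about 128 events by month 62 (50 + 12), whereas the plan speaks of 90. A constant loss hazard of about 0.036 per month (an assumption) brings the no-switch count to 90 at month 62. The table repeats step 3 with and without that loss. It assumes 3 patients per month continue to be randomized until 50 months after the switch.

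Analysed events and power at the 90th Group 1 event:

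| Switch | Both arms dropped, no loss | MT-401 only, no loss | Both arms dropped, with loss | MT-401 only, with loss |
|---|---|---|---|---|
| Month 6 | 73, 72% | 82, 77% | 79, 75% | 85, 78% |
| Month 12 | 57, 62% | 75, 73% | 67, 68% | 80, 76% |
| Month 18 | 42, 49% | 68, 69% | 56, 60% | 75, 73% |

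Changing one assumption at a time from the first column gives 73 to 82 events and 72% to 77% at month 6; changing both gives 85 events and 78%. The MT-401-only columns use the equal-allocation formula and are slightly optimistic, because the arms are then no longer 1:1.

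**5. Interim.** Analysed events at the 45th Group 1 event, in the same column order: 31, 39, 34 and 40 for a month-6 switch; 18, 33, 24 and 36 for a month-12 switch.

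**6. Does replacement to 150 cure it?** Not under the literal trigger. With a month-6 switch and no loss, only about 3 × (44.9 − 6) ≈ 117 of the 150 evaluable patients have been randomized when the 90th Group 1 event occurs.

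**The case against.** The strongest reply is that Group 1 in the trigger sentences merely distinguishes the adjuvant part from Group 2. The operative SAP sections name no population, efficacy is assigned to the All Randomized set, and the 80% is stated for 90 events at the primary analysis. On that reading the events are counted in the analysis set and power stays at 80.5% to 80.9%. This reading is open, and it stands as a limit on the point. It does not remove it: Protocol 9.3, 9.5.1 and 4.1 and SAP 6.1 attach the counts to Group 1, and Table 8 treats the analysis set as a subset of Group 1.

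A reader might infer three stronger conclusions that the documents do not support.
- **That the trial is underpowered as planned.** The shortfall requires an optional switch, made after Group 1 patients have been randomized and had events, together with the literal reading of the trigger.
- **That excluding patients found to be MRD-positive costs events even without a switch.** SAP 7.2 removes those patients from Group 1 itself, so their events need not count toward the trigger.
- **That one specific power loss can be quoted.** No switch date or loss rate is given. The replacement text concerns patients not treated with the final product, and SoC patients receive none, so it is unclear whether pre-switch SoC patients are dropped. Protocol 4.3.3 and 4.3.4 also let enrolled but untreated patients receive the new product, which could shrink the affected group.

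The interim consequence is also limited: the futility rule is non-binding, and the DMC charter may add criteria.

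**Conclusion.** The point holds conditionally. The counting population for the 45 and 90 events is not tied to the RFS analysis set. If the Sponsor changes the product after Group 1 randomization begins, the literal trigger runs the primary test with fewer than 90 analysed events and below 80% power. Power was below 80% in every switch scenario calculated. Over the four combinations of assumptions, a month-6 switch gives about 73 to 85 events and 72% to 78%, and a month-12 switch about 57 to 80 events and 62% to 76%. These are scenarios under exponential RFS at the plan's accrual rate, not predictions. Without a switch, or if the events are in fact counted in the analysis set, there is essentially no loss. The ambiguity should be settled before the interim, since the plan foresees the switch and adjusts patients for it but not events.

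**What to change.** State in Protocol 9.3, 9.5.1, 4.1 and the synopsis, and in SAP 6.1, 7.4.4 and 7.4.7.3, that the 45 and 90 RFS events, the information fraction and the conditional power are all counted in the All Randomized analysis set (final dose and process). State also whether SoC patients randomized before a switch belong to that set, and what happens at the interim if the final product has not yet been fixed. Keeping pre-switch SoC patients while dropping pre-switch MT-401 patients would save events but leave the arms neither concurrent nor 1:1, so that choice needs a reason.

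The cost is a sentence or two in each place and, after a switch, later analyses. If both arms restart at the switch, the 90th analysed event comes later than the no-switch date by the switch time: under the no-loss model, about month 51 instead of month 45 for a month-6 switch, and about month 57 for a month-12 switch. No extra patients are needed, because the 150 evaluable patients already planned supply the events.
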